10.6.2 Safety

Safety variables will be analyzed separately for the period between a) Screening and Baseline, b) for the period between Baseline and Month 9, c) for the period between Baseline and final assessment (Month 18 or date of premature withdrawal from the study), d) as well as for the total treatment period (Screening to Month 18). For the randomized treatment period, analyses will be performed according to the treatment group into which the patients were randomized.

All analyzes of safety parameters will be based on the safety population. Corresponding data from the NRP group will be described similarly for the period between Screening and Baseline visit.

The key safety variables which will be analyzed will be as follows.

- Incidence and severity of infections, in particular clinically apparent CMV
- Incidence and severity of Adverse Events (AEs) and Serious Adverse Events (SAEs)
- Incidence of AEs leading to discontinuation from the study
- Relative frequency of abnormal vital signs measurements and laboratory parameters

The incidence rates for (serious) adverse events and infections will be analyzed by treatment group.

AEs/Infections

Generally, infections data are analyzed together with AE data. In addition, infection data will be analyzed separately.

Data collected by AE CRFs and by Infection CRFs and CMV-CRFs are to be coded with the MedDRA dictionary that gives preferred term and body system information. The incidence of AEs will be summarized by body system, preferred term, severity, and relationship to study drug. All information pertaining to AEs noted during the study will be listed by treatment group and patient, detailing verbatim given by the investigator, the preferred term, the body system, start/end dates, severity and drug-relatedness. The AE onset will also be shown relative (in number of days) to the day of initial dose per study period (within the first 3 months, after Baseline (Month 6)).

In addition to being analyzed similarly as AEs, as described above, the relative frequency of infection by type and micro-organism will be tabulated. AEs occurring 7 or more days after the discontinuation of study medication will not be included in AE/infection summary tables.

Laboratory data

Abnormalities according notable criteria (see [Appendix 2](#)) will be identified. The proportions of patients with clinically notable abnormalities according to the notable criteria will be summarized. Shift tables describing changes from status prior transplantation (Month 0) and Baseline based on the expanded normal limits will be

presented for treatment endpoints (study Month 6 and 18) and worst observations during the different study periods (up to Month 6 as well as between Month 6 and Month 18). The worst observation is defined as the highest or lowest measure during the different observations periods whereby high or low are chosen according to the direction of abnormality (e.g. the highest will be chosen for serum creatinine, the lowest for leukocytes). Further, descriptive statistics of change from baseline of all laboratory variables will be presented by visit. A by-patient listing of all laboratory data (with clinically notable abnormalities being flagged) will be generated. Only assessments obtained up to 2 days after the discontinuation of study medication will be considered “on-treatment” and analyzed with relationship to Everolimus.

Vital signs

Vital signs variables include measurements of oral body temperature, systolic and diastolic blood pressures, pulse and body weight. Vital signs will be examined for abnormal values and change from Baseline according to pre-specified clinically notable criteria (see [Appendix 2](#)). Appropriate incidence rates of clinically notable abnormalities for between-group differences will be provided. Further, descriptive statistics of change from baseline of all vital signs variables will be presented by visit. A by-patient listing of all vital signs (with clinically notable abnormalities being flagged) will be generated. Shift tables describing changes from baseline based on clinically notable criteria will be presented for treatment endpoint (Month 18) and worst on-treatment observations. Only assessments obtained up to 2 days after the discontinuation of study medication will be considered “on-treatment”.

10.6.4 Tolerability

In addition to the analysis of the primary outcome variable of renal safety and tolerability, the following will be analyzed:

- Renal function as assessed by Cockcroft-Gault at month 18 after Tx
- Serum creatinine and creatinine slope (1/serum creatinine versus time) including the treatment period between BL (Month 6) and Month 18

Analyses of renal function as determined by other calculations (serum creatinine, glomerular filtration rate (GFR, Cockcroft-Gault)) will be evaluated in the same manner as described for the primary outcome measure.

In addition to quantitative analyses, the frequency distributions of patients with an improved GFR at study Month 18 compared to BL (Month 6) will be compared between the two regimens.

The creatinine slope (1 / serum creatinine versus time) will be determined from all assessments between Month 6 and Month 18 (both visits included) using a linear regression model. These slopes will be compared with a two-sided Wilcoxon rank-sum test between the treatment groups.

Additionally, tolerability of study medication will be assessed from the rate of patients who withdraw prematurely from study medication or in whom study medication had to be converted to another immunosuppressive regimen due to abnormal laboratory

results, adverse events, or toxicity. A number of reasons are pre-defined in [section 7.7](#) of this protocol. The frequency distribution of these reasons will be presented with absolute and percent values. The most frequent reasons (total $n \geq 5$) for discontinuation and/or conversion as well as the total number of patients who are affected by such intolerance of study medication will be compared between the two treatment groups using the exact Fisher test.

10.6.5 Resource utilization

The treatment costs which arise from hospitalization, immunosuppressants, dialysis and concomitant medication will be performed separately by the Health Economics Department of Novartis. Results will be added in an Appendix to the Clinical Study Report.

10.6.6 Health-related Quality of Life

No health-related Quality of Life assessments are planned to be performed in this study.

10.6.7 Pharmacokinetics

Analysis of the Cyclosporin A, Tacrolimus and Everolimus blood levels will be done by treatment group and separately for the treatment phases (up to and after Month 6), the NRP group will be analyzed.

Everolimus

Mean blood level values of Everolimus will be presented in tabular form for each timepoint (visit window) and as mean value over time. Trough values will be tried to be kept in a therapeutic window of 5 – 10 ng/mL during the whole study. The number of patients with deviations from the therapeutic window will be counted (separately for values “below” and “above” therapeutic range) and tabulated per visit and in total.

Patients with any trough level value outside the therapeutic window will be described in detail by narratives reporting also Everolimus dose level and dose adjustments, if applicable.

Cyclosporin A

Mean blood level values of Cyclosporin A will be presented in tabular form for each timepoint and as mean value over time. Blood levels will be tried to be kept in therapeutic windows. The number of patients with deviations from the therapeutic window (see [section 6.5.2](#)) will be counted and tabulated per visit and in total.

In the CNI-free group mean blood level values of cyclosporin A will be presented in tabular form for each assessment up to Month 8.

Tacrolimus

Mean blood level values of Cyclosporin A will be presented in tabular form for each timepoint and as mean value over time. Blood levels will be tried to be kept in

therapeutic windows. The number of patients with deviations from the therapeutic window (see [section 6.5.2](#)) will be counted and tabulated per visit and in total.

In the CNI-free group mean blood level values of Tacrolimus will be presented in tabular form for each assessment up to Month 8.

10.6.8 Pharmacogenetics/pharmacogenomics

No measurements of pharmacogenetics/pharmacogenomics will be done in this trial.

10.6.9 Biomarkers

No biomarkers will be assessed in this trial.

10.7. Interim analysis

No interim analysis is planned.

10.8 Sample size calculation

The probable difference between the CNI-free - and the CNI-group in the GFR is estimated as $\delta = 8$ ml/min with $\sigma = 16$ ml/min. With $\alpha=.05$ (two sided significance level) and $1-\beta = 90\%$ (power), $n=86$ patients per group are required to demonstrate superior efficacy of the CNI-free regimen compared to the CNI-group in the GFR using the t-test [REDACTED]. To compensate for some uncertainty of the assumptions for sample size calculation, the calculated sample size is increased by $\approx 15\%$. Therefore, a total number of $N=200$ patients ($n=100$ per treatment group) will be randomized and treated in both treatment arms after Baseline (Month 6 post Tx).

In order to achieve the planned number of randomized patients as exactly as possible which may be hampered by the delay between inclusion (Screening – Month 3 post Tx) and randomization (Baseline - Month 6 post Tx), the rate of non-randomized patients will be determined when 150 patients will be randomized, and extrapolated to a number of 200 randomized patients. Recruitment will be stopped, when 200 patients + 120% of the extrapolated rate of non-randomized patients will be included at Screening. The further 20% of non-randomized patients are considered as a safety margin to avoid underrecruitment of randomized patients.

According to amendment 4, enrollment into this study will be terminated by 31st December 2015, by that time about 165 patients will have been recruited into this trial. Under the assumptions above, this would lead to a power of 82%. Since this sample size will contain also patients who discontinued the trial/medication early or who had other protocol deviations, the actual power will even be somewhat lower.

Under the assumptions specified in the initial protocol, the study will still have 82% power with the now reduced sample size. That means that the scientific value will not

be compromised with 82% probability. However, even if the study should just fail to reach statistical significance, it will most likely still show the presence (or absence) of a non-significant trend, which would contribute to the body of evidence for this treatment option.

11 Discussion and rationale for study design features

A parallel group design is the most appropriate model to show differences between two treatments. The design includes an initial phase of 3 months during which patients are treated according to center standard outside the trial and an additional 3-months Run in phase with a Cyclosporin A or Tacrolimus based immunosuppressive regimen which is required by clinical needs.

Therapy switch from the CNI-based to the CNI-free regimen after randomization follows experiences from previous clinical trials as well as the recommendations of the second German-Austrian Certican Consensus Conference ([Rothenburger et al., 2007b](#), see [section 1](#) of this protocol).

Blinding of the two study treatments was not reasonable in this trial because dosing of Everolimus,, Tacrolimus and Cyclosporin A has to be based upon trough levels. Therefore the study has to be planned open-label. However, the endpoint of the study is GFR which is an objective outcome variable depending on laboratory measures. An influence of open-label treatment on this primary outcome variable is limited because dosing behavior will mainly be governed by drug trough levels but only in a few expected cases of renal toxicity by the creatinine level.

The randomization visit at Month 6 was scheduled at a time-point after Tx when the adaption of the individual organism to the graft is considered stable, on average of all transplant patients. It is to be expected that the immunological risk at this timepoint is lower, and the benefit of CNI elimination will continue. For this purpose, a CNI-free regimen will be compared with a CNI based immunosuppressive regimen. It is expected, that the CNI-free regimen will result in a superior renal function when compared to the CNI -based regimen, while it is as safe and effective as the CNI-based regimen with regard to occurrence of biopsy proven acute rejection episodes of ISHLT 1990 grade $\geq 3A$ resp. ISHLT 2004 grade $\geq 2R$, acute rejection episodes associated with hemodynamic compromise, graft loss / re-transplant, death, and lost to follow up, as well as of treatment failure (composite endpoint).

A maintenance treatment period of about 9 months under the two regimens, CNI-based versus CNI-free, is considered sufficiently long to explore any differences between both groups in the glomerular filtration rate, which is the primary outcome measure.

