Amendment 3

Amendment rationale

In response to German health authority's request, the protocol was modified to implement most recent notifications for use of MPA based on the dear health care professional letter (DHCPL) that was sent out for CellCept® by Roche on 12-Dec-2014. In detail the study medication stopping rules were adopted to clearly follow the recommendations given in the DHCPL. This information was added to sections 6.5.1 (Study drug administration), 6.5.2 (Permitted study drug adjustments), 6.5.6 (Premature patient withdrawal from study treatment) and to Appendix 5 (Dose Reduction of Everolimus and MPA).

Further, two exclusion criteria were amended for enhanced study feasibility in line with clinical praxis and patients' de facto condition as follows:

Exclusion criterion 10 (enrollment) and exclusion criterion 4 (baseline) were modified to allow for inclusion of patients with leukocytes $\geq 3000/\text{mm}^3$ (see Protocol Synopsis and Section 5).

Exclusion criterion 17 (enrollment) was removed. (see Protocol Synopsis and Section 5).

Corrections of typos were made for clarification of visit schedule (see Section 7, Table 7.1).

Changes to specific sections of the protocol are shown in the track changes version of the protocol using **strike through red font for deletions** and **red underlined for insertions**.

This amended protocol will be sent to the Institutional Review Board (IRBs)/Independent Ethics Committee (IECs) and Health Authorities for approval. The changes described in this amended protocol require IEC approval prior to implementation.

Amendment 4

Amendment rationale

This amendment addresses the size of study population. In the study protocol 200 patients were intended to be randomized. Recruitment of study has been ongoing since 2009. Due to ongoing slow recruitment the planned sample size of 200 patients cannot be achieved in a considerable amount of time. Thus, enrollment will be terminated by 31st December 2015. At timepoint of preparation of this amendment 4 to protocol n = 160 patients have been randomized into this study.

A comment was added to section 10.8. (Sample size calculation)

Further, in response to German Health Authority's request, the protocol was modified to implement most recent notifications for use of MPA based on the dear health care professional letter (DHCPL) that was sent out for CellCept® by Roche 10-Nov-2015.

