### 1.1 Study design

This was a prospective, multi-center, randomized, controlled, parallel group, open label study in heart transplant recipients. Enrollment was terminated at 31st December 2015 with a protocol amendment. At that time 162 de novo heart transplant patients have been randomized to the two treatment groups at Baseline visit (Month 6 post Tx). The patients were recruited from 9 transplant centers in Germany.

During the first three months post Tx the patients may have been treated according to center standards. Latest after study inclusion (Month 3 post Tx ±2 weeks), the patients received an immunosuppressive regimen consisting of Cyclosporin A (based on C0-h level) or Tacrolimus (based on C0-h level) + Everolimus (target C0-h level: 5 – 10 ng/mL) or MPA + corticosteroids.

At Month 6 (±1 week) post transplantation (Baseline), patients whose eligibility was confirmed by additional in- and exclusion criteria were randomized and hence allocated to one of the two treatment groups in a 1:1 ratio in the following way:

A randomization list was produced under the responsibility of Novartis Biometrics Department using a validated system that automates the random assignment of treatment groups to randomization numbers in the specified 1:1 ratio (CNI group, CNI-free group). The randomization scheme was reviewed and locked after approval. According to the recommendations given in the ICH E9 Guideline “Statistical Principles for Clinical Trials” (CPMP, 1998), the used block length was specified in a separate document which was withheld from the study centers. The randomization list was kept sealed in a secure location.

At Baseline visit (Month 6 post Tx), all eligible patients were given a randomization number that assigns them to one of the treatment groups. The randomization numbers were sequentially allocated to the patients per center in the order of inclusion in the randomized treatment period.

Randomization of individual patients was performed centrally by a CRO. Allocation of a patient to one of the two treatment groups was performed in the following steps.

1. Information about patient enrollment (Screening Visit – Month 3 post Tx): Study sites informed the randomization department of the CRO about each patient inclusion via fax.

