## **3 Sample size calculation**

The probable difference between the CNI-free - and the CNI-group in the GFR was estimated as  $\delta = 8 \text{ ml/min}$  with  $\sigma = 16 \text{ ml/min}$ . With  $\alpha=.05$  (two sided significance level) and  $1-\beta = 90\%$  (power),  $n=86$  patients per group were required to demonstrate superior efficacy of the CNI-free regimen compared to the CNI-group in the GFR using the t-test [REDACTED]. To compensate for some uncertainty of the assumptions for sample size calculation, the calculated sample size was increased by  $\approx 15\%$ . Therefore, a total number of  $N=200$  patients ( $n=100$  per treatment group) were initially planned to be randomized and treated in both treatment arms after Baseline (Month 6 post Tx).

According to amendment 4, enrollment into this study was terminated by 31st December 2015, by that time about 165 patients had been recruited into this trial. Under the assumptions above, this would lead to a power of 82%. Since this sample size also contains patients who discontinued the trial/medication early or who had other protocol deviations, the actual power was even somewhat lower.

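### The 82% power stated for about 165 patients does not follow from the protocol's own assumptions, which give about 89%

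*Protocol*

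**What the plan says.** Protocol section 10.8 plans for a GFR difference of 8 ml/min with a standard deviation of 16 ml/min, two-sided alpha 0.05 and 90% power. It uses a t-test and arrives at 86 patients per group, raised by about 15% to 100 per group.

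Text added with Amendment 4 then covers the early end of enrolment at about 165 patients: "Under the assumptions above, this would lead to a power of 82"%. The next sentence says that the sample includes patients who stopped early or deviated from the protocol, so that "the actual power will even be somewhat lower". The following paragraph refers again to the assumptions of the initial protocol and says that "the study will still have 82% power with the now reduced sample size". It adds that the scientific value will not "be compromised with 82% probability".

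SAP section 3 carries the figure forward: "by that time about 165 patients had been recruited into this trial. Under the assumptions above, this would lead to a power of 82"%. It also repeats that discontinuations and deviations made the actual power lower. SAP section 1.1 gives the final count: "At that time 162 de novo heart transplant patients have been randomized to the two treatment groups".

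**The concern.** The inconsistency shows before any calculation. The protocol says that 2 × 86 = 172 patients give 90% power, and then that about 165 patients under the same assumptions give 82%. Losing 7 of 172 patients (4%) cannot cost 8 points of power.

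The stakes are limited. The rationale for Amendment 4 gives recruitment as the reason for stopping ("Due to ongoing slow recruitment the planned sample size of 200 patients cannot be achieved in a considerable amount of time"), so the power figure did not drive that decision. It is, however, the only number in either document that bears on whether the reduced sample is adequate. A reader cannot tell whether it is an arithmetic slip or hides an allowance for loss that is not stated.

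**Working it through.** **Inputs.** From Protocol 10.8: δ = 8 ml/min, σ = 16 ml/min (δ/σ = 0.5), two-sided α = 0.05, two-sample t-test, about 165 patients. From Protocol 6.3: 1:1 allocation. From the Amendment 4 rationale: 160 randomized when the amendment was prepared. From SAP 1.1: 162 randomized in the end. Neither document gives the split between arms, so near-equal arms are assumed and then varied.

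**Formula.** Noncentrality λ = δ / [σ √(1/n₁ + 1/n₂)], with n₁ + n₂ − 2 degrees of freedom. Power is the probability that a noncentral t variable with that λ falls outside ± the 97.5th percentile of the central t.

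**Step 1: reproduce the original sample size.**
- 85 + 85: λ = 0.5/√(2/85) = 3.260, df 168, power 89.99%.
- 86 + 86: λ = 0.5/√(2/86) = 3.279, df 170, power 90.32%.

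So 86 per group is the smallest equal group size that reaches 90%. This is the protocol's own figure, which confirms the method.

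**Step 2: apply the same calculation to the reduced sample.**

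| Patients | Split | λ | Power |
|---|---|---|---|
| 165 (Protocol 10.8, SAP 3) | 82 + 83 | 3.211 | 89.11% |
| 162 (SAP 1.1) | 81 + 81 | 3.182 | 88.55% |
| 160 (Amendment 4 rationale) | 80 + 80 | 3.162 | 88.16% |

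The normal approximation for 82 + 83 is Φ(3.211 − 1.960) = Φ(1.251) = 89.5%, so the choice of method does not matter.

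**Step 3: find what 82% corresponds to.**
- 67 + 67 gives 81.93% and 68 + 68 gives 82.50%. The stated power therefore fits about 134 patients, and (165 − 134)/165 = 18.8% fewer than 165.
- With 165 patients, 82% would need an SD of about 17.8 instead of 16, or a difference of about 7.2 instead of 8.

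**Step 4: try other explanations.**
- *Unequal arms.* With 162 patients, 71 + 91 still gives 88.07%. It takes about 47 + 115 (81.88%) to reach 82%, which is not credible under 1:1 randomization in blocks.
- *Recruited meaning enrolled rather than randomized.* The 160 already randomized give 88.16%.
- *A stricter alpha.* Two-sided 0.025 at 82 + 83 gives 82.8%, but the stated level is two-sided 0.05.
- *Loss already deducted.* 165 × 0.85 ≈ 140 patients gives 83.6%, and 165 × 0.80 = 132 gives 81.4%. No such rate is stated, and the sentence after the 82% deducts for discontinuations and deviations again.

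**The case against.** The strongest reply is that the error is harmless. It understates power, so nobody is led to trust the trial too much. It enters no endpoint, model, analysis set or decision rule, there is no interim analysis or sample size re-estimation that could use it, and enrolment was over before the SAP was written. All of this is true, and it limits the weight of the point. It does not make the figure right.

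A second reply is that 82% may include an allowance that the text leaves out. Section 10.8 already uses a margin of about 15% for uncertainty in its assumptions, and taking a similar margin off 165 leaves about 140 to 143 patients and a power of about 83.6% to 84.5%. That is nearer to 82% than to 89%, but it is not a match. Section 10.8 also ties the figure twice to the original assumptions and then lowers the power again for loss. Some text after the mention of the t-test is redacted, but 86 per group reproduces without it. What stands is that the documents do not show how 82% arose, so the sponsor should be free to state its basis instead of replacing it.

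A third reply is that neither 89.1% nor 88.5% is the power of the planned primary analysis. That analysis is an ANCOVA on baseline GFR and center, in a full analysis set that excludes patients without post-baseline GFR. This is fair as far as it goes. The corrected figure should be labelled as t-test power under the planning assumptions, before exclusions. It does not rescue 82%, which the plan attributes to those same t-test assumptions.

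**Conclusion.** The concern holds. Under the stated assumptions, power is 89.1% for 165 patients and about 88.5% for the 162 randomized, against a stated 82%. The shortfall is about 7 points at 165. The result rests on the protocol's own difference, SD, alpha and test, and on near-equal arms; a split as uneven as 71:91 moves it only to 88.1%. It is one wrong number, given three times in Protocol 10.8 and once in SAP 3. It should be corrected because it is certain and easily checked, not because any conclusion of the trial depends on it.

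**What to change.** In Protocol 10.8, replace 82% with about 89% for about 165 patients in all three places. In SAP 3, give about 88.5% for the 162 randomized, assuming roughly equal arms, and label it as t-test power under the planning assumptions before exclusions. Keep the sentence in each document that discontinuations and deviations lower the actual power.

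If 82% was meant to allow for loss, which would have to be about 18–19% of 165, state that rate and delete the sentence that lowers the power a second time.

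The cost is one number in three places in the protocol and one in the SAP, plus a short label. It needs no extra patients and no change to any analysis.
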